5.2.1 Dictionaries

Medications and therapies will be coded using the World Health Organization drug dictionary (WHODRUG Global B3 Sep 2019 or later).

Adverse events will be coded using the Medical Dictionary for Regulatory Activities (MedDRA®) version 22.1 or higher.

5.2.2 Baseline values

The **baseline value** is defined to be the last non-missing value which was assessed before the first dose of investigational treatment.

- If an assessment date, but not time, is collected, and the assessment date is the same as the date of first dose of investigational treatment, that assessment will be used to derive the baseline value (if it is non-missing).
- If the assessment time is collected, and the time of the first dose of investigational treatment is collected, and the assessment date is the same as the date of first dose of investigational treatment, that assessment may only be used to derive the baseline value if the assessment time is prior or equal to the start of administration of investigational treatment.
- If multiple assessments are collected on the same day, without recorded time of assessment, the algorithm in Section 5.8(d)(iii) will be followed.

Change from baseline is defined as the post-baseline value minus the baseline value, and will be missing if the baseline value is missing.

Percent change from baseline is defined as $100^* (\text{change from baseline})/\text{baseline value}$. If the baseline value and post-baseline value are both 0, the percent change from baseline will be set to 0. If the baseline value is 0, or missing, and the post-baseline value is non-zero, the percent change from baseline will be set to missing.

5.2.3 Dosage calculations

Cumulative dose (mg) is calculated as the sum of all doses administered to a subject.

Actual dose intensity (mg/cycle) is calculated as cumulative dose / number of cycles initiated.

Cumulative planned dose (mg) is calculated as the sum of planned doses for each treatment administration visit in which respective dose is administered.

Planned dose intensity (mg/cycle) is cumulative planned dose / number of cycles initiated (as per Section 5.4).

Relative dose intensity is calculated as $100 * \text{actual dose intensity} / \text{planned dose intensity}$.

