11.3 Treatments

The safety set will be used for the analyses below. Categorical data will be summarized as frequencies and percentages. For continuous data, mean, standard deviation, median, 25th and 75th percentiles, minimum, and maximum will be presented.

The duration of exposure in months to GEN3009 and combination with GEN3013, as well as the dose intensity (computed as the ratio of actual cumulative dose received and actual duration of exposure) will be summarized by means of descriptive statistics.

The number of subjects with dose adjustments and the reasons will be summarized, and all dosing data will be listed.

Concomitant medications will be summarized.

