1.1 Preface

The objective of this document is to detail the statistical methodology to be used for the interim and final statistical analyses of the Dose Escalation part and the Dose Expansion part of study GCT3009-01.

This statistical analysis plan (SAP) covers the analysis of both parts of the trial and is based on the following information and documents:

Trial Protocol	16 Dec 2019; v 4.0 (Amendment 2)
Unique Case Report Forms (CRFs)	19 Feb 2019; v1.0

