3.8 Randomization, blinding and unblinding procedures

Subjects are assigned to intravenous GEN3009 with defined doses (for the Dose Escalation part) or at the RP2D dose level (for the Dose Expansion part), as described in the protocol. No randomization is performed.

This is an open-label trial; therefore no blinding of treatment will be performed.

4 Analysis Sets

The assignment of subjects to the different analysis sets will be finalized prior to database snapshot (for the Dose Escalation part or Dose Expansion part as appropriate), based on a review of the data that is agnostic to dose level cohort, where applicable. This review is typically performed during a data review meeting but may also be performed via independent review of analysis set assignments by team members. Approval of final analysis set inclusion will be documented prior to the database snapshot. All subjects excluded from the different analysis sets will be listed, along with the reason for exclusion.

Screen Failures Analysis Set

The screening failure analysis set includes all subjects who were screened but not enrolled. Subjects who were rescreened and subsequently enrolled will be excluded from this analysis set.

Full Analysis Set (FAS)

The FAS comprises all subjects to whom trial drug has been assigned and who received at least 1 dose of GEN3009. Subjects will be analyzed according to their assigned treatment/dose (dose level and regimen planned).

Pharmacokinetic Analysis Set (PAS)

The PAS includes all subjects who have been exposed to GEN3009 and have had at least one pharmacokinetic sample collected that has provided a valid bioanalytical result. All subjects will be classified according to the dose level and treatment schedule which they received.

Safety Set (SAF)

The safety set consists of all subjects who receive at least 1 dose of GEN3009. Subjects will be classified according to actual treatment received.

Subjects who were treated with more than dose level and treatment schedule by mistake will be classified according to the dose level and treatment schedule they received the longest, or the highest dose level (in the case of equal durations). Subjects with a dose reduction due to adverse event will be classified according to the original dose level and treatment schedule.

Should the FAS and SAF coincide, the analyses that are planned to be presented for both will be based on the SAF only.

Dose-Determining Analysis Set (DDS)

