5.3.3 Progressive Disease

Progressive disease must be confirmed by 2 consecutive scans, at least 4 weeks apart, as described in protocol 9.2.3.2.

5.4 *Calculation of durations and times to events*

Duration of an event occurring on or after first dose date, in days, is calculated as event end date – event start date + 1.

Durations in weeks will be calculated as durations in days divided by 7.

Durations in months will be calculated as durations in days divided by 30.4375.

Time from initial diagnosis will be calculated in months, from the initial diagnosis of the primary site to the first dose date: (first dose date – date of first diagnosis) /30.4375

Time from last anti-CD20 therapy to treatment with GEN3009 will be calculated in months, from the latest treatment end date of any agent administered as part of the last prior anti-lymphoma treatment that included an anti-CD20 compound to the first dose date: (first dose date – date of last anti-CD20 therapy +1) /30.4375

Total number of months on trial will be calculated as: (last contact date – first dose date + 1)/30.4375

Follow-up time will be calculated, in weeks, as: (date of last disease assessment by investigator – first dose date + 1) / 7.

Total treatment duration will be calculated in days as:

- If last cycle is Cycle 1, 2 or 3: last dose date – first dose date + 7
- If last cycle is Cycle 4 – 9: last dose date – first dose date + 14
- If last cycle is Cycle 10 or later: last dose date – first dose date + 28

Progression-free survival (PFS)

PFS is defined as the time in days from Day 1 of Cycle 1 to the day (+1) of first documented disease progression, or the day (+1) of death due to any cause, whichever comes first. Progression does not require confirmation (per Lugano criteria). PFS censoring will be based on Table C1 in Appendix C in the FDA Guidance for Industry: Clinical Trial Endpoints for the Approval of Non-small Cell Lung Cancer Drugs and Biologics [4].

Duration of response (DOR) will be calculated in days as:

DOR = date of first documented progressive disease or death from any cause – date of first response + 1.

In the absence of progressive disease or death, responders will be censored per the FDA censoring rule utilized for PFS, as presented in Appendix I. First response is defined as first documented occurrence of CR or PR (including any complete responses pending confirmation). DOR will only be calculated for those subjects achieving CR or PR.

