- For events, medications, or conditions beginning on the date of first dose of trial medication, the start time will be imputed as the time of the start of the first dose of trial medication, unless partial information indicates otherwise, in which case it will be imputed as 00:00.
- All partial or missing start times on other days will be imputed as the earliest possible time.

Incomplete end times will be imputed as 23:59.

5.8 *Observation and analysis times*

Subject information may be presented by cycle day or study day, as appropriate.

Study days

Study day is defined as the number of days between the first dose of trial medication and a particular date, and is calculated as:

- Study day = Assessment date – Date of first dose of trial medication, where assessment date is before the date of first dose
- Study day = Assessment date – Date of first dose of trial medication + 1, where assessment date is on or after the date of first dose

Therefore, the date of the first dose of trial medication will be Day 1, and the day immediately prior will be Day -1.

Cycle days

Cycle day is presented by both cycle number and day number, where C2D1 represents Day 1 of Cycle 2. The first dose of trial medication for a given cycle is considered Day 1 of that cycle, and cycle day in general are calculated as for study day:

- Cycle day = Assessment date – Date of first dose of trial medication + 1, where assessment date is on or after the date of first dose

Cycle day is not defined for dates prior to the first dose of trial medication, or for dates greater than 28 days after the last dose of trial medication. In infrequent cases, a new cycle might be delayed; the days between the 28th day of the last cycle and the 1st day of the new cycle will be considered off-cycle days, and cycle day will not be defined. If a new cycle starts slightly earlier than the planned day for any reason, the first day of dosing in that cycle will be considered Cycle x Day 1, and the prior cycle will have <28 days.

Trial periods

For the Dose Escalation part only, the DLT assessment period (also referred to as the DLT observation period) is defined as 28 days from Cycle 1 Day 1, as per protocol 7.1. Therefore, this period will run from Cycle 1 Day 1 through Cycle 1 Day 28.

The trial participation period is divided into three mutually exclusive segments:

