8.2 Dosage and Treatment Duration

Descriptive statistics for the number of cycles initiated will be presented overall and by dose level cohort or diagnosis cohort (as appropriate).

The cumulative dose, actual dose intensity, cumulative planned dose, planned dose intensity, relative dose intensity, and treatment duration will be presented by cohort, separately for Cycles 1-3, 4-9, and 10+. The completion status and withdrawal reasons (withdrew due to AE, withdrew due to PD, or withdrew due to other reason), and subjects with dose adjustments (reductions,

interruptions, or permanent discontinuations) and reasons for adjustments, will be summarized by treatment cycle and cohort.

The total treatment duration and total number of days in trial will be summarized by cohort.

Follow-up time will be calculated, as the time from first dose of trial treatment until the last contact date or date of death, whichever comes last. Follow-up time will be summarized with univariate statistics, without adjusting for censoring, and presented using mean, median, SD, minimum and maximum.

Exposure information will be listed by subject.

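### Relative dose intensity in SAP 5.2.3 cannot register skipped or late doses, because planned dose counts only dosed visits and no time term enters

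*SAP*

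**What the plan says.** SAP 5.2.3 builds RDI in steps. Cumulative dose is everything the subject received. Then: "Actual dose intensity (mg/cycle) is calculated as cumulative dose / number of cycles initiated". The planned counterpart starts from this sum: "Cumulative planned dose (mg) is calculated as the sum of planned doses for each treatment administration visit in which respective dose is administered". That sum is then divided by the same count of cycles to give planned dose intensity, and RDI is 100 times actual over planned intensity.

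SAP 8.2 sets out the display: "relative dose intensity, and treatment duration will be presented by cohort, separately for Cycles 1-3, 4-9, and 10" and later. It also tabulates cycles initiated, and reductions, interruptions and permanent discontinuations with reasons, and it lists exposure by subject. SAP 5.4 takes total treatment duration from calendar dates: last dose minus first dose, plus 7, 14 or 28 days according to the last cycle.

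Protocol 11.3 (v7.0) defines dose intensity differently, as a quantity "computed as the ratio of actual cumulative dose received and actual duration of exposure". Protocol Tables 17 and 18 list dose intensity next to interruptions and delays, under the primary objectives in Dose Escalation and the secondary objectives in monotherapy Expansion. RDI is not named in the protocol.

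**The concern.** A reader of an RDI column expects the share of the scheduled dose that was delivered on schedule. In this trial, departures from schedule come mainly from holding and postponing doses. Protocol 7.4.1, 7.4.2.1 and 7.4.3.1 provide for both, and 7.4.2.1 does not allow GEN3009 dose reduction in Expansion. As written, RDI does not respond to holds or postponements. What can move it is an incomplete infusion, a dosing error or a dose reduction. The SAP foresees reductions in its Safety Set definition (Section 4): "Subjects with a dose reduction due to adverse event will be classified according to the original dose level and treatment schedule".

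At stake is a column that sits at or near 100% almost by construction, beside tables of interruptions that seem to say otherwise. The planned mg/cycle column does not help, because it falls in step with the actual one when doses are skipped.

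**Working it through.** The plan gives no RDI value to reproduce, so the check is algebra followed by worked patterns.

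**Algebra.** Let G be the total dose given, P the planned dose summed over dosed visits, and c the cycles initiated.

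RDI = 100 x (G/c) / (P/c) = 100 x G/P.

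The SAP points to 5.4 for c, and that section does not define it, but c cancels. If k full doses of size D are given, RDI = 100 x kD/kD = 100% for any k. No date or duration appears.

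**Inputs.**
- SAP 3.5: Days 1, 8, 15 and 22 in Cycles 1-3, so 12 doses.
- The last nominal dose, C3D22, is study day 28 + 28 + 22 = 78. Planned duration is 78 - 1 + 7 = 84 days.
- The dose D is a flat amount. The mg values are redacted, but D cancels.
- The skip and delay patterns are assumed. The longer delays use protocol limits. In Escalation the limit is 4 weeks from the last dose: C1D22 plus 28 days is Day 50, against a Cycle 2 due date of Day 29, so 21 days late. In Expansion it is 4 weeks from the scheduled date, so 28 days late.

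**Comparison.** Share of schedule = (dose given / actual duration) / (12D / 84).

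| Pattern, Cycles 1-3 | Actual mg/cycle | SAP planned mg/cycle | SAP RDI | Share of schedule |
|---|---|---|---|---|
| 12 of 12, on time | 4D | 4D | 100% | 100% |
| Day 8 skipped in each cycle (9 of 12) | 3D | 3D | 100% | (9/84)/(12/84) = 75.0% |
| Days 8 and 15 skipped in each cycle (6 of 12) | 2D | 2D | 100% | 6/12 = 50.0% |
| 12 of 12, Cycle 2 late by 14 days | 4D | 4D | 100% | 84/98 = 85.7% |
| 12 of 12, Cycle 2 late by 21 days | 4D | 4D | 100% | 84/105 = 80.0% |
| 12 of 12, Cycle 2 late by 28 days | 4D | 4D | 100% | 84/112 = 75.0% |
| Day 8 skips and 14 days late | 3D | 3D | 100% | (9/98)/(12/84) = 64.3% |
| 12 of 12, one half infusion | 3.83D | 4D | 11.5/12 = 95.8% | 95.8% |
| Day 8 skips and one half infusion | 2.83D | 3D | 8.5/9 = 94.4% | 8.5/12 = 70.8% |

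Actual mg/cycle falls with skips. It does not fall with late cycles, because its divisor counts cycles and does not measure time.

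**Alternative reading.** Suppose the planned-dose sentence was meant to cover every visit at which a dose is scheduled. Nine of 12 would then give 75%, but 12 of 12 with a late cycle would still give 12/12 = 100%. The wording does not support that reading, and it repairs only half the problem.

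**The case against.** The best defence is that little depends on this column. No hypothesis is tested, RDI is not a protocol endpoint, and SAP 8.2 reports the ingredients elsewhere. Skips show in actual mg/cycle and in the interruption summary, and delays lengthen treatment duration. A reader might infer that the protocol's dose-intensity endpoint is lost or that missed doses go unreported, and the documents do not support either. That part of the defence stands and limits the point. It is weaker for delays: SAP 8.2 does not name them among the adjustments, so a late cycle shows only indirectly, through duration.

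A second defence is that dose given over dose planned at dosed visits is a legitimate measure of infusion completeness. It responds to infusions cut short and does not penalise subjects who stop early. That is fair, but the SAP labels the result relative dose intensity, and under that name it will be read as adherence to schedule.

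Third, no document gives a skip or delay rate, and protocol 2.1.4.1 reports that neutrophil counts usually recovered by the next dose. Patterns such as 6 of 12 doses therefore show how the formula behaves and do not forecast results.

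**Conclusion.** The definition is wrong as written for a measure called relative dose intensity: full doses give 100% however many are skipped and however late they are. The conclusion follows from the literal formula and needs no assumption about dose. The sizes (75% for 9 of 12; 85.7% for a 14-day delay) rest on the assumed patterns. The effect is confined to cumulative planned dose, planned dose intensity and RDI in descriptive tables. Severity is minor to moderate.

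Two stronger readings should not be drawn. A reader might blame the cycle-day rule in SAP 5.8, under which "the days between the 28th day of the last cycle and the 1st day of the new cycle will be considered off-cycle days". That rule governs day labels only; the divisor would be the same count of cycles without it. A reader might also infer that the SAP departs from its own protocol on dose intensity. The SAP was written to protocol v4.0, whose text is not among the documents, so the mismatch with protocol 11.3 is shown only between the current documents.

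**What to change.** Replace the planned-dose and intensity definitions in SAP 5.2.3 with:

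1. Cumulative planned dose = sum of protocol-scheduled doses at every nominal cycle/day visit from C1D1 through the nominal visit of the last dose given, whether or not each was given. A postponed visit counts once.
2. Actual dose intensity = cumulative dose / (last dose date - first dose date + 7, 14 or 28 days). This uses the duration in SAP 5.4 and agrees with protocol 11.3.
3. Planned dose intensity = cumulative planned dose / (nominal study day of that same visit - 1 + the same interval).
4. RDI = 100 x (2) / (3).

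With Day 8 skipped in Cycles 1-3 this gives (9D/84)/(12D/84) = 75%. With Cycle 2 late by 14 days and all 12 doses given, it gives (12D/98)/(12D/84) = 85.7%. It needs only dosing dates and the schedule.

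State the limitation in the table footnote: doses missed after the last dose given do not lower this RDI. If C3D8, C3D15 and C3D22 are all missed and treatment ends, the result is (9D/63)/(9D/63) = 100%, and the loss must be read from the interruption and discontinuation tables. Ending the count at the decision to stop would catch such doses, but the documents do not show that this date is collected. The result would also depend on the due date given to a held dose. Take four doses in Cycle 1, C2D1 held, and treatment stopped on Day 57. If the calendar runs on, 4 of 8 gives 50%. If only C2D1 is due, the result is (4/35)/(5/35) = 80% or (4/63)/(5/35) = 44.4%, according to whether its date is Day 29 or Day 57.

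For the cycle-block tables, set the last-dose cut-off once per subject over all treatment, and say which block takes the days before a late Cycle 4 or Cycle 10. When the SAP is updated to protocol v7.0, compute RDI separately for GEN3009 and GEN3013, each against its own protocol schedule.

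The cost is a few sentences and minor programming. Reported RDI will be lower than under the present rule wherever doses before the last one given were skipped or late.

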3 OBJECTIVES AND ENDPOINTS

Objectives and related endpoints are described for the Dose Escalation in [Table 17](#) and for the Expansion in [Table 18](#), [Table 19](#), and [Table 20](#).

Table 17 Objectives and Endpoints for Dose Escalation (GEN3009 for R/R B-cell NHL Including CLL/SLL)

OBJECTIVES	ENDPOINTS
Primary	

• Determine the MTD with and/or determine the RP2D of GEN3009• Evaluate safety and tolerability of GEN3009	
• Rate of DLTs• Frequency and severity of adverse events (AEs)/AESIs/SAEs• Changes in laboratory parameters• Changes in vital signs• Frequency of dose interruptions, dose delays, and dose intensity
Secondary	

• Establish PK profile of GEN3009• Evaluate immunogenicity of GEN3009• Evaluate preliminary anti-tumor efficacy of GEN3009• Evaluate preliminary clinical efficacy of GEN3009	
• PK parameters: clearance, volume of distribution and area under the curve (AUC) at different time points ($AUC_{7\text{days}}$, AUC_{last} and AUC_{inf}), maximum concentration (C_{max}), time to C_{max} (T_{max}), predose trough concentrations (C_{trough}), and half-life ($T_{1/2}$)• Incidence of neutralizing anti-GEN3009 antibodies (ie, ADAs)• ORR• CR rate• DoR• TTR• PFS• OS
Exploratory	

• Assess potential biomarkers predictive of clinical response to GEN3009 and evaluate potential surrogacy with PFS and OS• Assess pharmacodynamic markers related to MoA of GEN3009	
• CD37 expression• Minimal residual disease (MRD) status• Pharmacodynamic markers in blood samples (leukocyte subset frequencies and phenotype, target antigen expression, complement regulatory protein expression, plasma complement levels and activation [CH50], and cytokine levels)

Table 18 Objectives and Endpoints for Expansion (GEN3009 for R/R, DLBCL, FL, and CLL Cohorts)

OBJECTIVES	ENDPOINTS
Primary	
• Evaluate (preliminary) anti-tumor efficacy of GEN3009	• ORR
Secondary	
• Establish PK profile of GEN3009	• PK parameters: CL, AUC _{7days} , AUC _{last} , C _{max} , T _{max} , C _{trough} and T _{1/2}
• Evaluate safety and tolerability of GEN3009	• Frequency and severity of AEs/AESIs/SAEs • Changes in laboratory parameters • Changes in vital signs • Frequency of dose interruptions, dose delays, and dose intensity
• Evaluate clinical efficacy of GEN3009	• CR rate • DoR • TTR • PFS • OS

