11.1 Adverse events

Adverse events (AE) will be coded using MedDRA, and the National Cancer Institute Common Terminology Criteria for AEs (CTCAE criteria v5.0 or higher). They will be presented by primary System Organ Class (SOC) and Preferred Term (PT), or by PT only (in descending order) by dose cohort and overall. Subjects will be summarized at most one time per SOC and at most one time per PT, unless otherwise specified.

Adverse events are collected from the first GEN3009 dose until 30 days after the last GEN3009 dose. Treatment-emergent adverse events (TEAEs) are defined as AEs which begin, or worsen, during the on-treatment period ending 4 weeks after the last dose of trial medication as defined in Section 5.4. Adverse events collected during the post-treatment period will be flagged in data listings, and excluded from summaries, and will not be categorized as TEAEs.

The following summaries of TEAEs will be presented:

- All TEAEs, by SOC and PT
- All TEAEs, by PT, in order of descending frequency
- Serious TEAEs adverse events (SAEs), by SOC and PT
- Non-serious TEAEs, by SOC and PT
- TEAEs of CTCAE grade 3 or higher, by SOC and PT
- Non-serious TEAEs of CTCAE grade 3 or higher, by SOC and PT
- Related non-serious TEAEs of CTCAE grade 3 or higher, by SOC and PT
- TEAEs leading to dose reduction or dose interruption, by SOC and PT
- TEAEs leading to permanent discontinuation of trial treatment, by SOC and PT
- TEAEs by SOC, PT, and severity, where subjects are presented at the highest recorded severity level within SOC and PT
- Related TEAEs, by SOC and PT
- Related serious TEAEs, by SOC and PT
- TEAEs by SOC, PT, and relationship, where subjects are presented at the highest recorded relationship within SOC and PT

- Fatal TEAEs

The following tables will also be presented by overall ADA status, as per Section 11.8.

- Non-serious TEAEs of CTCAE grade 3 or higher, by SOC and PT
- Fatal TEAEs

All adverse events will be listed by subject, with those beginning during the post-treatment period flagged. Additional listings will be presented for all SAEs, all AEs leading to withdrawal of treatment, non-serious AEs of grade 3 or higher, and fatal AEs.

In addition, adverse events will be presented graphically by the incidence of AEs over infusion number, and using a swim lane plot to monitor the severity of AEs over time.

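### Relative dose intensity in SAP 5.2.3 cannot register omitted or delayed doses, and the SAP's dose intensity has no time term

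*SAP*

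**What the plan says.** **SAP 5.2.3.** Cumulative dose is the total a subject received. For the intensity: "Actual dose intensity (mg/cycle) is calculated as cumulative dose / number of cycles initiated". For the comparator: "Cumulative planned dose (mg) is calculated as the sum of planned doses for each treatment administration visit in which respective dose is administered". Planned intensity divides that planned sum by the same number of cycles, and relative dose intensity is 100 times actual over planned. SAP 8.2 reports all of these by cohort, together with treatment duration, separately for Cycles 1-3, 4-9 and 10 onward.

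**Time in the SAP.** SAP 5.4 derives a total treatment duration from dosing dates: "If last cycle is Cycle 1, 2 or 3: last dose date – first dose date + 7", with 14 or 28 days added in the later blocks. SAP 5.2.3 does not use it. Under SAP 5.8, when a new cycle starts late, the days from the end of the previous 28-day cycle up to "the 1st day of the new cycle will be considered off-cycle days, and cycle day will not be defined".

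**Protocol.** Section 11.3 reads: "dose intensity (computed as the ratio of actual cumulative dose received and actual duration of exposure". Table 17 places "Frequency of dose interruptions, dose delays, and dose intensity" among the primary endpoints for Dose Escalation, and Section 11.4.1.1.3 refers to 11.3 for it. Section 7.4.2.1 bars GEN3009 dose reduction in Expansion and permits delay of up to 4 weeks past the scheduled date. Section 7.4.1 permits postponement in Dose Escalation to 4 weeks after the last dose. Table 25 has doses held for cytopenias in all cohorts.

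**Versions.** SAP 1.1 and 2.1 tie the SAP to protocol v4.0 (Amendment 2). The protocol supplied is v7.0 (Amendment 5).

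**The concern.** Relative dose intensity is the SAP's one ratio of delivered to planned dose, and a reader of the exposure table will take 100% to mean that the schedule was kept. In this regimen toxicity is handled mainly by holding or postponing doses rather than by reducing them. A ratio that counts only visits with a dose, and has no clock, misses those modifications. It moves only when a given dose differs from plan, as with an incomplete infusion or a dosing error.

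Protocol 4.3.1 rests the weekly schedule on sustained target saturation, so whether a cohort could keep that schedule is a substantive part of tolerability. At stake is the description of tolerability by dose level and by indication: a cohort that missed a quarter of its doses would look fully dosed, while one half-given infusion would show as a shortfall.

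**Working it through.** Neither document states a numerical dose intensity, so there is no figure to reproduce.

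**Inputs**
- Schedule in Cycles 1-3: Days 1, 8, 15 and 22 of 28-day cycles, so 12 doses (SAP 3.5).
- On-schedule last dose, C3D22: study day 2 × 28 + 22 = 78. By SAP 5.4, duration = 78 − 1 + 7 = 84 days.
- Delay limits without medical monitor approval: 28 days past the scheduled date in Expansion (protocol 7.4.2.1). In Dose Escalation, 4 weeks from the last dose less the 7-day interval gives 28 − 7 = 21 days (protocol 7.4.1).
- Dose per infusion set to 1 (an assumption, since the doses are redacted). It cancels in the ratios.

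**Step 1: what the SAP ratio reduces to.** Let D be the sum of doses given, P the sum of planned doses at visits where a dose was given, and C the cycles started.

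Relative dose intensity = 100 × (D/C) / (P/C) = 100 × D/P.

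An omitted visit drops out of both D and P. No date enters either. If every given dose is full, D = P and the result is 100%.

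**Step 2: comparison with dose over time.** With T the elapsed days, the time-based figure is 100 × (D/T) / (12/84). Protocol 11.3 gives only the absolute ratio D/T; expressing it relative to the on-schedule value is my comparator. The omission rows assume that the last dose, C3D22, was given.

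| Cycles 1-3 | D | T (days) | Dose per cycle (D/3) | SAP relative dose intensity | Scheduled-dose denominator only (D/12) | Time-based |
|---|---|---|---|---|---|---|
| On schedule | 12 | 84 | 4.00 | 100% | 100% | 100% |
| 1 infusion half given | 11.5 | 84 | 3.83 | 95.8% | 95.8% | 95.8% |
| 1 omitted, last kept | 11 | 84 | 3.67 | 100% | 91.7% | 91.7% |
| 3 omitted, last kept | 9 | 84 | 3.00 | 100% | 75% | 75% |
| 21-day delay, all given | 12 | 105 | 4.00 | 100% | 100% | 80% |
| 28-day delay, all given | 12 | 112 | 4.00 | 100% | 100% | 75% |
| 28-day delay and 3 omitted, last kept | 9 | 112 | 3.00 | 100% | 75% | 56.3% |

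For example, three omitted: (9/84)/(12/84) = 0.75. 28-day delay: (12/112)/(12/84) = 84/112 = 0.75. Both: (9/112)/(12/84) = 0.5625.

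Two things follow. Dose per cycle falls with omissions but stays at 4.00 for a pure delay. Changing the denominator to scheduled doses repairs omissions but still returns 100% for delays.

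**Step 3: omissions at the end of treatment.** The SAP 5.4 duration stops at the last dose actually given.
- C3D22 omitted: last dose on day 71, T = 71 − 1 + 7 = 77, and 11/77 = 1/7 = 12/84, so 100%.
- Last three doses omitted: last dose on day 57, T = 57 − 1 + 7 = 63, and 9/63 = 1/7, so 100%.

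Using the SAP 5.4 duration unchanged would therefore hide trailing omissions. Running actual and planned duration to the end of Cycle 3 (84 days) gives (11/84)/(12/84) = 91.7% and (9/84)/(12/84) = 75%.

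**The case against.** The strongest reply is that nothing is hidden. SAP 8.2 puts cumulative dose, dose per cycle, cycles started and treatment duration in the same summary and lists exposure by subject. With flat doses, omissions lower the mg per cycle and delays lengthen the duration. That stands, so a reader who infers that tolerability information is lost goes too far. What is missing is a defined measure that combines dose and time, and the one ratio that appears to do so reads 100%.

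A second reply is that relative dose intensity is not a protocol measure. True, but the SAP defines it and reports it by cohort, so it should mean what its name says. Reading the planned-dose rule as covering scheduled doses is not what the text says, and would leave the delay rows at 100%.

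A reader might also infer that the SAP breached protocol 11.3. The documents do not support that. The v4.0 wording is not supplied, and the change log says of Section 11 only that it was revised. The SAP's own list of Dose Escalation primary endpoints (SAP Section 11) contains neither delays nor dose intensity, which fits their having been added later.

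Finally, a reader might infer that held doses will be lost among infusion stops for infusion-related reactions, because SAP 8.2 covers reductions, "interruptions, or permanent discontinuations) and reasons for adjustments, will be summarized by treatment cycle and cohort", and SAP 11.1 lists "TEAEs leading to dose reduction or dose interruption, by SOC and PT", neither naming delays. This too is unsupported. The SAP does not define interruption, which could include held doses; the tabulated reasons can separate the two; protocol 11.3 itself promises only dose adjustments with reasons; and the table shells are to follow the SAP. It forms no part of this point.

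**Conclusion.** The point holds for relative dose intensity as SAP 5.2.3 is written, whatever the protocol version: the measure cannot register an omitted or delayed dose. In Cycles 1-3 it reads 100% where dose over time reads 75% (three doses omitted, or a 28-day delay), 80% (21-day delay) or 56.3% (28-day delay with three omitted). The separate observation, that mg per cycle has no time term and does not match the current protocol 11.3, is correct as a comparison of the two texts, with version lag a possible cause.

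These figures rest on the literal reading of the planned-dose rule, on the last dose being given in the omission cases, on delays at the protocol limits, and on the on-schedule comparator described above. The documents give no frequency of omissions or delays, so the number of subjects affected is not estimated. The effect is confined to descriptive tolerability summaries: no test, DLT count or escalation rule changes. It is worth correcting before the exposure tables are programmed.

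**What to change.** In SAP 5.2.3:
- **Actual dose intensity:** cumulative dose divided by actual treatment duration, counted in elapsed days as in SAP 5.4, so that off-cycle days are included.
- **Planned dose intensity:** all doses scheduled through one stated endpoint (treatment discontinuation or the end of the last cycle started), whether or not given, divided by the planned duration of that schedule. Count scheduled doses by protocol visit.
- **Common endpoint:** for this purpose, take actual duration to the same endpoint instead of stopping at the last dose, so that trailing omissions count.
- **Relative dose intensity:** the ratio of the two.
- **Cycle blocks:** SAP 5.4 gives only a total duration, so state how duration is formed for Cycles 1-3, 4-9 and 10 onward, and which block takes off-cycle days falling between blocks.
- **Cycles started:** SAP 5.2.3 refers to SAP 5.4 for this count, but 5.4 does not define it. Add the definition if the per-cycle figure is kept.

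Check the dose-intensity wording of protocol v4.0. If it differs from the current 11.3, make the change when the SAP is brought up to the current protocol.

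The cost is SAP wording and minor programming from dosing dates already collected and listed. No new data, visits or subjects are needed.
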